4.2. Removal of Subject From Therapy

If a subject is withdrawn from the study, the Investigator will complete and report the observations as thoroughly as possible up to the date of withdrawal including the date of last treatment and the reason for withdrawal.

If the subject is withdrawn due to an AE, the Investigator will follow the subject until the AE has resolved or stabilized.

Subjects can only be considered for surgical resection after the completion of Part 1.

If a subject undergoes surgical resection of the tumor after Part 1, the study treatment is recommended to be discontinued 1-3 weeks before the surgery. The subject will be followed for surgery and its outcome and not considered as discontinued from the study. Data collection for the surgery and its outcome may continue in a separate protocol. If a subject undergoes surgical resection prior to completion of Part 1, the information about surgery and its outcome will still be collected.

4.2.1. Reasons for Withdrawal/Early Discontinuation

The reasons a subject may discontinue or be withdrawn from the study permanently include but are not limited to:

- AE
- Disease progression
- Subject request
- Investigator decision
- Protocol violation
- Subject noncompliance
- Pregnancy
- Study termination by the Sponsor or IRB/IEC
- Subject transition to commercial pexidartinib

During Part 2, if a subject experiences radiologic progression documented by central read, the subject may either be withdrawn from the study or, if the subject is continuing to have clinical benefit, the Investigator may consult with the Sponsor's Medical Monitor or designee to allow the subject to remain in the study.

4.2.2. Withdrawal Procedures

When a subject discontinues or is permanently withdrawn from the study, the Investigator will notify the Sponsor and ensure that the procedures listed in the 28 Day "Post-treatment Visit" column in the Schedule of Events ([Table 15.2](#) and [Table 15.3](#)) are performed 28 ± 7 days after the

subject's last dose of study treatment and prior to initiating any new PVNS/GCT-TS therapy, including surgery.

The consequence of a subject's withdrawal of all consent will be that no new information will be collected from that subject and added to the existing data or any database. However, every effort will be made to follow all subjects for safety.

The reason for study withdrawal will be recorded. If a subject discontinues study treatment to undergo surgery, information about the type of surgery and its outcome will be collected.

If a subject discontinues study treatment before the end of Part 1, the end of Part 1 assessments (Part 1 Completion visit/Early Termination visit) should be performed at the time of early discontinuation (Table 15.2). These subjects will not be unblinded.

4.2.3. Subject Replacement

Subjects withdrawn from the study will not be replaced.

4.3. Subject Re-screening Procedures

Re-screening is permitted for any candidate who failed to meet eligibility criteria upon initial screening. If rescreened, the candidate will not be given a new subject identification number. The initial screening information and the reason why the subject is ineligible for the initial evaluation will be recorded on the Screening Log. No data from the initial evaluation will be entered into the clinical database for a subject who is rescreened. However, MRI, ROM and surgical assessment may not need to be repeated, following consultation with Sponsor Medical Monitor.

5. TREATMENTS ADMINISTERED

5.1. Investigational Products

The study treatment, pexidartinib (PLX3397), is an HCl salt supplied in 200 mg-strength immediate-release capsules for oral administration.

The placebo capsules for this trial have an identical qualitative composition to the PLX3397 HCl capsules except no active pharmaceutical ingredient is included. The amount of mannitol is increased in the placebo blend to compensate for amount of active ingredient that is not added.

The placebo and pexidartinib capsules are identical in appearance to maintain the blind during Part 1.

5.2. Study Treatment Administration

Study treatment will only be given to randomized subjects under the supervision of the Principal Investigator or identified sub-Investigator(s). The study treatment for home administration during Part 1 will be dispensed to the subject for the first time at the P1-C1D1 visit (within 3 days of randomization), and the study treatment for home administration during Part 2 will be dispensed to the subject for the first time at the P2-C1D1 visit. Capsules should be swallowed and not crushed, chewed, or dissolved in liquid. In Part 1, subjects will receive either pexidartinib or matching placebo capsules. In Part 2, subjects will receive only pexidartinib capsules.

Study treatment administration will begin at the P1-C1D1 visit in the morning. At that visit, subjects will be instructed to take five capsules a day for the first 2 weeks; 1000 mg/d pexidartinib or matching placebo, this amount will be divided into a morning dose of two capsules and an evening dose of three capsules. After 2 weeks (at the P1-C1D15 visit), the dose will be reduced to two capsules in the morning and two capsules in the evening, 800 mg/d pexidartinib or matching placebo. Subjects who had a dose reduction during the first 2 weeks will continue treatment at their reduced dose. Doses should be taken in the fasting state (ie, no food for 1 hour before and 2 hours after dose administration). During the fasting period, subjects will be permitted to eat a low-fat snack (eg, crackers, toast, tea) if needed. Doses will be taken at approximately the same times of the day and approximately 12 hours apart. Each dosing cycle will be 28 days.

For the P1-C1D15 and P2-C1D15 visits and any visit when an ECG will be performed, subjects should be told to NOT take their morning dose of study treatment before coming to their study visit, which should be scheduled for the morning; instead, they should be told to bring their bottle of study treatment to the clinic and take their morning dose upon instruction by the study site. The time of dosing will be recorded. Subjects will then take their evening dose at home. If dose administered in the clinic is taken in the afternoon, then the subject should be instructed to skip their evening dose for that day.

For the P2-C1D1 visit (Week 25), subjects should be told to NOT take the morning dose of study treatment before their visit and to bring all unused capsules to the clinic for accountability. Subjects who will continue into Part 2 will be given open-label pexidartinib for the first time at

that visit, taking the same number of capsules per day as they were taking at the end of Part 1, ie, a maximum dose of 800 mg/d pexidartinib.

Between clinic visits, subjects will administer their study treatment at home and record the dosing information in the study dosing diary. Missed doses (those generally outside of a \pm 2-hour dosing window) should be skipped and NOT administered as a double dose at the next dosing time point. Subjects who vomit their dose should be instructed NOT to make up that dose.

Further details on study treatment administration are contained in the separate Pharmacy Manual.

For subjects who undergo surgical resection of their tumor, study treatment will be discontinued before surgery and will not be restarted after surgery.

5.3. Dose Modification Guidelines

In both Parts 1 and 2, reducing or interrupting the dose for toxicity may take place at any time according to the guidelines in [Table 5.1](#) and [Table 5.2](#). Dose reduction/interruption guidelines for hematologic and non-hematologic treatment-related TEAEs are based on severity. Dose interruptions can be implemented at the discretion of the treating physician to manage intolerable or clinically significant toxicity. If a dose interruption is required, study assessments should be performed as scheduled, irrespective of the study treatment delay, with the exception of PK assessments which should be deferred until treatment is resumed. Interruptions due to toxicity lasting >14 d require treatment discontinuation unless the medical monitor approves continuation.

When an odd number of capsules a day are to be taken, the larger number of capsules should be taken as the evening dose. For example, 600 mg/d or matching placebo = 3 capsules (1 capsule in the morning, 2 capsules in the evening). When an even number of capsules per day is to be taken, the morning and evening doses should be the same (eg, 800 mg/d or matching placebo = 4 capsules (2 capsules in the morning, 2 capsules in the evening) or 400 mg/d or matching placebo = 2 capsules (1 capsule in the morning, 1 capsule in the evening).

Dose reductions should be applied in increments of 200 mg/d or matching placebo (one capsule), with a maximum total reduction of 600 mg/d or matching placebo (ie, a minimum dose of 400 mg/d or matching placebo). Subjects unable to tolerate 400 mg/d or matching placebo (two capsules) will be discontinued. Once dose reduction takes place for toxicity, a dose re-escalation is generally not allowed unless approved after discussion with the Sponsor's Medical Monitor or designee.

Dose-modification guidelines for treatment-emergent toxicities as well as guidelines for their management are presented [Table 5.1](#) and [Table 5.2](#). These parameters are only a guide and are not intended to supersede the clinical judgment of the treating physician. All adjustments should be communicated to the Sponsor's Medical Monitor or designee. Rechallenge with a reduced dose of pexidartinib may result in a recurrence of increased serum transaminases, bilirubin, or ALP. Monitor liver tests weekly for the first month after rechallenge.

Table 5.1: Dose Modification Guidelines for Treatment-emergent Toxicities

Event	Severity	Pexidartinib Dosage Modifications
Hepatotoxicity		
Increased ALT and/or AST	>3 to 5 × ULN	
 Withhold and monitor liver tests weekly. If AST and ALT ≤3 × ULN within 4 weeks, resume at reduced dose. If AST or ALT not ≤3 × ULN in 4 weeks, permanently discontinue pexidartinib.
	>5 to 10 × ULN	
 Withhold and monitor liver tests twice weekly. If AST and ALT ≤3 × ULN within 4 weeks, resume at reduced dose. If AST or ALT not ≤3 × ULN in 4 weeks, permanently discontinue pexidartinib.
	>10 × ULN	
 Permanently discontinue pexidartinib. Monitor liver tests twice weekly until AST or ALT ≤5 × ULN, then weekly until ≤3 × ULN.
Increased ALP ^a and GGT	ALP >2 × ULN with GGT >2 × ULN	
 Permanently discontinue pexidartinib. Monitor liver tests twice weekly until ALP ≤5 times ULN, then weekly until ≤2 × ULN.
Increased bilirubin	TB >ULN to <2 × ULN or DB >ULN and <1.5 × ULN	
 Withhold and monitor liver tests twice weekly. If an alternate cause for increased bilirubin is confirmed and bilirubin <ULN within 4 weeks, resume at reduced dose. If bilirubin not <ULN in 4 weeks, permanently discontinue pexidartinib.
	TB ≥2 × ULN or DB >1.5 × ULN	
 Permanently discontinue pexidartinib. Monitor liver tests twice weekly until bilirubin ≤ULN.
Adverse Reactions or Other Laboratory Abnormalities		
Any	Severe or intolerable	
 Withhold until improvement or resolution. Resume at a reduced dose upon improvement or resolution.

ALT = alanine aminotransferase; ALP = alkaline phosphatase; AST = aspartate aminotransferase; DB = direct bilirubin; GGT = gamma-glutamyl transferase; TB = total bilirubin; ULN = upper limit of normal.

^a Confirm ALP elevations as liver isozyme fraction.

Table 5.2: Additional Liver Evaluation

Evaluation	Comments
Increase frequency of testing liver chemistries to twice per week, including INR, and continue until liver chemistries have stabilized, and then reduce to weekly until liver chemistries return to normal or baseline	Investigational treatment may be started after liver function tests recover to Grade 0 to 1 or baseline level, and in consultation with Medical Monitor
Detailed history focusing on medications and substances used: alcohol, change in medication dosages, new medications added, attention to use of acetaminophen, OTC medication use and recreational drug use. Check for change in diet or use of dietary supplements, with particular attention to dose and duration of any herbal product	Suspect medications will be discontinued or substituted for if possible
Detailed medical history and physical exam seeking new abnormalities	Evaluate abnormalities found
Full serological evaluation for hepatitis A, B, C and E (IgG and IgM). Check for autoimmune hepatitis with serological laboratory studies	If viral hepatitis or autoimmune hepatitis suggested, have subject evaluated by hepatologist
Liver ultrasound performed to evaluate liver and biliary tree	Evaluate any abnormalities found
Check history for exposure to chemical agents	Remove chemical exposure and have subject seen by hepatologist
Obtain hepatology consult if liver function continues to rise beyond 14 days	Contact Medical Monitor
We request that cases be discussed with the Medical Monitor whenever investigational product is being held for liver function test abnormality.	

Ig = Immunoglobulin; INR = international normalized ratio; OTC = over-the-counter.

For suspected cases of cholestatic liver injury (eg, aminotransferase increase concurrent with hyperbilirubinemia, or liver biopsy suggesting cholestasis and/or ductopenia), patients will be followed to assess long-term outcome. Additional diagnostic and follow-up procedures might be implemented as appropriate to fully assess the event.

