6.5. Study Procedures

The Investigator should conduct the study in compliance with the protocol agreed to by Sponsor and, if required, by the regulatory authority(ies), and that was given approval/favorable opinion by the IRB/IEC.

A deviation to any protocol procedure, or a waiver to any stated criteria will not be allowed in this study except where necessary to eliminate immediate hazard(s) to the subject. Sponsor must be notified of all intended or unintended deviations to the protocol (eg, inclusion/exclusion criteria, dosing, missed study visits) on an expedited basis.

The Investigator, or person designated by the Investigator, should document and explain any deviation from the approved protocol.

If a subject was ineligible or received the incorrect dose or investigational treatment and had at least one administration of the study treatment, data should be collected for safety purposes, and the Sponsor's Medical Monitor or designee should be informed immediately.

The Investigator should notify the IRB/IEC of deviations from the protocol in accordance with local procedures.

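### For a subject enrolled with bilirubin at or above ULN, Tables 5.1 and 5.2 set different recovery targets after a bilirubin hold, and no visible text says which governs

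*Combined protocol and SAP*

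**What the plan says.** Section 5.3 of the protocol refers sites to Tables 5.1 and 5.2 together for dose changes and does not rank them.

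- **Table 5.1, lower bilirubin band** (total bilirubin above ULN and below 2 × ULN, or direct bilirubin above ULN and below 1.5 × ULN): drug is withheld. The resume line is "If an alternate cause for increased bilirubin is confirmed and bilirubin <ULN within 4 weeks, resume at reduced dose". The stop line is "If bilirubin not <ULN in 4 weeks, permanently discontinue pexidartinib".
- **Table 5.2, comment beside the testing-frequency row:** "Investigational treatment may be started after liver function tests recover to Grade 0 to 1 or baseline level, and in consultation with Medical Monitor".
- **Table 5.2, last row:** "We request that cases be discussed with the Medical Monitor whenever investigational product is being held for liver function test abnormality".
- **Section 4.1.1, criterion 9:** total bilirubin at entry may be as high as 1.5 × ULN.
- **Section 5.3, text:** a toxicity interruption of more than 14 days ends treatment unless the medical monitor approves continuation. Of the table parameters it says "These parameters are only a guide and are not intended to supersede the clinical judgment of the treating physician".
- **Hepatic safety update of December 2017** (end of Section 1): protocol-defined discontinuations should be followed, and rechallenge needs prior discussion with the Sponsor's Medical Monitor. The opening of this section is missing from the text available for review.

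**The concern.** A subject in the lower bilirubin band is on hold, so both tables speak to that subject. Table 5.1 measures recovery against ULN. Table 5.2 accepts a return to the subject's own baseline. When baseline is itself at or above ULN, the same week-4 result can mean a permanent stop in one table and a permitted restart in the other.

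At stake is re-exposure after a liver signal. The December 2017 update describes cholestatic injury that was sometimes severe and protracted, with liver dialysis, one transplantation, and one death with cholestatic injury still ongoing. Section 5.3 warns that rechallenge at a reduced dose may bring back raised transaminases, bilirubin or ALP. A stop rule for this drug should have one threshold.

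**Working it through.** The plan gives no figure on this point to reproduce. The check applies the two written rules to the same subject.

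**Inputs, in multiples of ULN**

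- *b*: baseline total bilirubin. Section 7.4 defines a safety baseline as the last non-missing value before first dose. I assume it respects the entry limit, so *b* ≤ 1.5 (Section 4.1.1). I use total bilirubin because criterion 9 sets no entry limit for direct bilirubin.
- Peak on treatment: inside the hold band, above 1.0 and below 2.0.
- *w*: total bilirubin at week 4. Other liver tests are taken as recovered.

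**Rules**

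- Table 5.1: permanent stop if *w* ≥ 1.0. Resume at a reduced dose if *w* < 1.0 and an alternate cause is confirmed.
- Table 5.2, baseline limb only: may start if *w* ≤ *b*, with the Medical Monitor consulted. The grade limb is left out because the documents give no grade cut-offs in multiples of ULN.

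The rules oppose each other when 1.0 ≤ *w* ≤ *b*. This requires *b* ≥ 1.0, so the region is 1.0 ≤ *w* ≤ *b* ≤ 1.5. The targets differ by *b* − 1.0, at most 1.5 − 1.0 = 0.5 × ULN.

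**Worked values** (peak 1.8, alternate cause confirmed)

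| *b* | *w* | Table 5.1 | Table 5.2, baseline limb | Opposed? |
|---|---|---|---|---|
| 0.9 | 0.9 | resume | may start | no |
| 0.99 | 0.99 | resume | may start | no |
| 1.0 | 1.0 | stop | may start | yes |
| 1.2 | 0.99 | resume | may start | no |
| 1.2 | 1.0 | stop | may start | yes |
| 1.2 | 1.2 | stop | may start | yes |
| 1.2 | 1.3 | stop | not met | no |
| 1.4 | 1.4 | stop | may start | yes |
| 1.5 | 1.5 | stop | may start | yes |

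A baseline of exactly 1.0 is included because Table 5.1 requires a value strictly below ULN. A confirmed alternate cause does not remove the conflict: the resume line needs both the cause and a value below ULN, while the stop line depends on bilirubin alone.

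**Immediate-stop rows.** Three hepatic rows of Table 5.1 stop drug at once: ALT or AST above 10 × ULN; ALP and GGT both above 2 × ULN; and total bilirubin at or above 2 × ULN or direct bilirubin above 1.5 × ULN. For the first, the table reads "Permanently discontinue pexidartinib. Monitor liver tests twice weekly until AST or ALT" and continues with monitoring targets. None of the three has a resume line. The Table 5.2 comment does not mention these subjects, so an explicit exclusion is absent, but no second recovery target competes with Table 5.1.

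**The case against.** The best defence is that Table 5.2 is a work-up table. Its comment is permissive, requires Medical Monitor consultation, and shares the table with a last row about product being held. On that reading it only adds conditions to a restart that Table 5.1 already allows. Other text points the same way. By day 28 the subject is 28 − 14 = 14 days past the point where treatment ends without monitor approval. Rechallenge needs prior discussion. Section 6.5 states "A deviation to any protocol procedure, or a waiver to any stated criteria will not be allowed in this study", except to remove an immediate hazard.

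Much of this stands, and it rules out several stronger readings that a reader might infer.

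- *That Table 5.2 reopens dosing for anyone permanently stopped, for example after ALT above 10 × ULN.* This requires a general permissive comment to override an explicit permanent stop. The natural reading is that Table 5.1 governs.
- *That a restart under Table 5.2 is open-ended in time.* The 14-day rule in Section 5.3 applies to it.
- *That everyone enrolled at 1.0 to 1.5 × ULN is caught.* The conflict also needs a hold in this band, a week-4 value back at entry level but not below ULN, and recovery of the other tests.
- *That the ALT/AST rows ("If AST or ALT not ≤3 × ULN in 4 weeks, permanently discontinue pexidartinib") conflict in the same way.* A full comparison needs grade cut-offs that the documents do not give, so I make no claim there.

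The defence does not settle the lower bilirubin row. That subject is held, so limiting Table 5.2 to held subjects leaves both targets in force. The monitor provisions say who must be consulted, not which threshold applies. The deviation rule does not decide it either, since a restart agreed under Table 5.2 would follow protocol text. The guide-only sentence covers both tables alike.

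**Conclusion.** The point holds for one row. In the lower bilirubin band, a subject with baseline total bilirubin of 1.0 to 1.5 × ULN, back at that level but not below ULN at week 4 and with other liver tests recovered, gets opposite dosing instructions from the two tables. The targets differ by up to 0.5 × ULN. For the immediate-stop rows the only gap is the missing explicit exclusion.

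This rests on the visible text, on the baseline limb alone, and on baseline respecting the entry limit. A ranking of the tables in the missing opening of the hepatic safety section would remove the point. The documents give neither hepatic event rates nor the share of subjects enrolled at or above ULN, so no count can be estimated; it may be small. Alpha, power and sample size are unaffected. It is a cheap improvement to a safety rule, with the practical risk already reduced by Medical Monitor involvement.

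**What to change.** Add to the restart comment in Table 5.2: *only where Table 5.1 permits resumption; not for subjects permanently discontinued under Table 5.1.* This makes below-ULN the single bilirubin target and supplies the missing exclusion for the immediate-stop rows.

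A subject enrolled at or above ULN would then have to fall below their own baseline to resume. If the sponsor's safety physicians prefer a baseline target for such subjects, they should write it into the lower bilirubin row of Table 5.1, so that one threshold still applies. That choice is clinical.

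The cost is a wording amendment and a letter to sites, with no new procedure or data. The downside is slightly less discretion, which the Table 5.1 stop lines already deny.

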5.3.1. Renal Impairment

A reduced dose of 600 mg/day (200 mg in the morning and 400 mg in the evening) is recommended in study subjects with mild to severe renal impairment (creatinine clearance [CL_{cr}] 15 to 89 mL/min estimated by Cockcroft-Gault using actual body weight).

5.4. Concomitant Medications

During the study, if the use of any concomitant treatment becomes necessary (eg, for treatment of an AE), the treatment must be recorded on the source document and electronic Case Report Form (eCRF), including the reason for treatment, name of the drug, dosage, route, and date of administration. All medications including prescription, over-the-counter (OTC), herbal and other nutritional vitamins and/or supplements taken within 28 days of P1-C1D1 will be recorded on the eCRF. Analgesic use and analgesic regimen will be recorded as described in Section 6.4.11.

Subjects enrolled in studies with pexidartinib who are also receiving concomitant warfarin should have their anti-coagulation status carefully monitored, especially shortly after initiation of pexidartinib, for the potential need to make adjustments in warfarin dosing. In particular, INR should be obtained just prior to initiation of pexidartinib, within 1 to 2 weeks after initiation, and periodically thereafter. Dose adjustments of warfarin should be made as medically indicated.

